6.1 Screen / Informed Consent Process

Patients considered to be eligible candidates for the study will be approached to understand their willingness and interest of volunteering for the study. The informed consent process will then be performed in the following manner:

Informed Consent

Informed consent will be obtained as outlined in 21 CFR Part 50 and the Good Clinical Practice: Consolidated Guidance (ICH, April 1996).

Eligible patients will be introduced to the study opportunity during a pre-operative visit. Patients will be given the opportunity to have their questions answered, either at the time of their visit, or after the visit via phone or email. Patients will be given the opportunity to provide consent at the time of their visit or at a later time if they need time to consider participating. A research study member at the approved study site will speak with the study candidate about the purpose of the study. Explanation of the study background, study procedure, follow up visit schedule, study procedure risks and benefits will be reviewed in detail with the patient. Patients will be given the time they need to read through the study information and informed consent document and ask as many questions as necessary to make them comfortable with the study and the requirements.

For those potential candidates who agree to participate in the study by signing the IRB approved Informed Consent Form (ICF), a baseline evaluation will be conducted. Consent may be obtained by the investigator or staff member authorized by the investigator.

If a patient does not have the capacity to give informed consent, they will be excluded from consideration for enrollment. If an enrolled subject loses the capacity to reasonably complete the study questionnaire surveys during the study, they shall be discharged from the study.

The investigator will ensure that prospective subjects have sufficient knowledge and comprehension of the information represented by the elements of informed consent to enable them to make an informed and enlightened decision whether or not to participate or allow participation in research. The investigator shall, based on clinical judgment, determine if the study candidate understood the information presented

The investigator shall be responsible for ensuring that valid consent is obtained and documented for all subjects. All study records including the completed consent forms and patient satisfaction questionnaires shall be maintained in a secure location in the investigator's clinic and handled in a manner that maintains confidentiality of the data.

6.2 Baseline Evaluation / Eligibility Determination / Enrollment

The study investigator or study staff member will conduct a formal evaluation for study eligibility which may include reviewing medical history and understanding general health. When the subject is determined eligible and scheduled for the arthroplasty procedure they will be enrolled into the study.

6.3 Random Assignment

The subject will be randomized to a closure assignment prior to the procedure. A study staff member will open a sealed randomization envelope consisting of closure assignment and a subject study identification number. The subject is considered enrolled into the study at this time and the subject disposition will be accounted for in study reports.

Subjects will be assigned in consecutive order in a 1:1 ratio for closure assignment (Metal Staples:Zip Closure Device) until all subjects are enrolled.

6.4 Procedure

Arthroplasty will be performed as standard and the assigned closure method will be applied and documented on the procedure Case Report Form (CRF). Subjects will be reminded of their follow-up visits to the study office.

6.5 Follow Up / Study Exit

The follow-up period of the study will begin after the arthroplasty procedure. All follow-up visits will be scheduled from the date of the arthroplasty procedure and should be within the study visit windows as indicated in the Table of Assessments (Table 1).

6.6 Study Evaluations and Assessments

The following assessments will be made during each study visit:

Subject Satisfaction Questionnaire – to evaluate subject experience and outcome of incision closure

POSAS (Patient and Observer Scar Assessment Scale) – the subject and investigator will rate commonly described scar characteristics from a patient and observers perspective.

Table 1: Schedule of Assessments

Assessments	Screening / Baseline	Study Procedure	3-Week Follow-Up (+/- 3 days)	6-Week Follow-Up (+/- 7 days)
Screen and Informed Consent Process	Х			
Medical Hx, Demographics, Eligibility	Х			
Randomization Assignment	Х			
Study Procedure and Closure Method		Х		
Subject Satisfaction Questionnaire			Х	Х
POSAS: Subject and Impartial rater Assessment			х	х
Photo of closure of incision		Х	Х	Х
Adverse Event review			Х	Х
Study Exit				Х

7 Subject Compensation

Participating study subjects will not incur any costs as a result of participating in the study and will not receive reimbursement or payments for participation.

8 Study Withdrawal

Subjects may be terminated or withdrawn from the study for the following reasons:

- Voluntary withdrawal meaning that the subject voluntarily chooses not to further participate in the study
- Lost to follow-up meaning that the subject is more than one month late (beyond the late visit window) to a study visit and 3 documented attempts to contact the subject are unsuccessful. A subject who misses a study visit but attends a subsequent visit will no longer be considered lost to follow-up.
- In the physician's opinion, it is not in the best interest of the subject to continue study participation.
- Subject death.

Any study subject who does not attend a scheduled follow-up visit should be contacted by site personnel to determine the reason for the missed appointment(s). The reason for the missed visit should be determined and documented in the subject's study records. All subjects enrolled (including those withdrawn or lost to follow-up) shall be accounted for with appropriate documentation.

9 Adverse Events

Adverse events (AEs) may occur during the procedure phase or the follow-up phase of the study. Adverse events occurring after the baseline assessment but before the arthroplasty procedure will be documented in the subject's medical record but will not count as related to the closure device.

Each adverse event will be recorded in the corresponding subject's CRF. Each adverse event will be judged by the Investigator as to its relationship and level of relatedness to the closure device. In addition, the Investigator will identify the date of onset, severity and duration of the AE. All adverse events will be monitored until they are adequately resolved or explained. If a subject reaches the final follow-up visit and is experiencing a new or ongoing adverse event, the study sponsor should be contacted to discuss the need and/or methods for continued surveillance of the event.

The Investigator must submit to the Sponsor a report of any Serious Adverse Event (SAE), Serious Adverse Device Effect (SADE) or Unanticipated Adverse Device Effect (UADE) within 24 hours of knowledge of the event.

Sponsor Contact: [name]
[contact]
[contact]

Email: [contact]

In addition, the Investigator will report adverse events to the reviewing IRB / EC (as applicable) according to the local reporting requirements.

10 Study Size Determination

Knee Arthroplasty: 2 groups: Zipline to Staples (2 groups, paired data) with POSAS Scale data est. delta \sim 1.5, and Est. SD \sim 1.41

Alpha error = .05

Power = 0.9, sample n = 19 pairs, or 38 total subjects with estimated 5% subject study loss, n = 40 total subjects, or 20 per group.

11 Methods and Procedures

- 1. Study investigator and designated staff shall be trained on study procedures by the sponsor or sponsor delegate.
- 2. Patients shall be screened prior to surgery for study eligibility by the investigator or staff member designated by the investigator.
- 3. Eligible patients shall be presented with the study opportunity during a pre-operative consultation visit to the study site, and will be given the opportunity to read the informed consent form and receive answers to any questions about the study. If the patient is able and willing to participate, they will sign the consent form and become an enrolled subject.
- 4. Randomization will be assigned in permuted block so that even numbers of each closure method is assigned
- 5. Immediately after the arthroplasty procedure the assigned closure method will be applied and documented on the procedure data form

- 6. During the subject's scheduled (i.e., standard of care) 3-week post-operative clinic visit and immediately AFTER the wound closure device is removed (e.g., Zip or staples), clinic staff will:
 - a. Administer the first patient satisfaction questionnaire
 - b. POSAS will be performed by an impartial rater
 - c. Photograph the scar in a well-lighted room at a distance of approximately 12-14", capturing the entire scar. Ensure the knee joint is flexed at approximately 45 degrees for the photo.
- 7. During the subject's scheduled (i.e., standard of care) 6-week post-operative clinic visit, clinic staff will:
 - a. Administer the second patient satisfaction survey
 - b. POSAS will be performed by an impartial rater
 - c. Photograph the scar in a well-lighted room at a distance of approximately 12-14", capturing the entire scar. Ensure the knee joint is flexed at approximately 45 degrees for the photo.
- 8. Once enrollment is complete and all subjects have completed the patient satisfaction questionnaires, the data will be analyzed and results will be evaluated by the investigator.

12 Risk/Benefit Assessment

Risk Category. This is a minimal risk study. The probability and magnitude of harm or discomfort anticipated in the research are not greater than those ordinarily encountered in daily life or during the performance of routine physical or psychological examinations or tests.

Potential risks associated with the use of the closure methods in this study as standard of care do not differ from those commonly used for closing wounds, incisions or lacerations.

Potential risks associated with the closure methods used in this study are listed below. Subjects will be monitored closely as part of this study to allow for detection of symptoms, should they be present. This, in turn, should allow for early treatment or intervention, if necessary.

The following are side effects that may occur as a result of use of closure methods used to repair incisions after the arthroplasty procedure:

- Blistering from overtightening of the Zip Closure Device causing excessive stretch force applied to the epidermis
- Edema which can cause skin shearing, skin blistering or loss of adhesion to occur
- Skin stripping upon removal as a result of any surgical tape or adhesive applied to skin
- Allergic reaction to the adhesive product including hypopigmentation or hyperpigmentation following removal
- Infection resulting from any bacteria introduced into the incision
- Dehiscence requiring intervention
- Device failure / malfunction
- Edema
- Wound site pain / discomfort
- Excessive scarring including:
 - Step-off
 - Contour irregularities
 - Excessive distortion
 - Poor cosmetic appearance

Protection Against Risks

This is a minimal risk study. Nonetheless, all efforts will be made to minimize any potential risk. Risks will be minimized through the use of an Investigator with a high degree of experience in orthopaedic surgery. The Investigator has received sponsor-led training in proper use of the device, prior to study initiation and as warranted throughout the study. The sponsor will monitor the study for any trends that would indicate a safety

issue.

Potential Risks to Patient Confidentiality

In all clinical studies, confidentiality of protected health information may be breached due to study-related activities beyond those of routine clinical care. This risk will be minimized by not collecting personally identifying information on Case Report Forms (CRFs) or other study-related documentation to be provided to the study sponsor

Potential Benefits to the Subjects

There are no potential benefits to the subjects other than the satisfaction of having helped improve the body of knowledge on the study subject, which may lead to future preference towards a superior wound closure modality in a subsequent surgery.

Alternatives to Participation

Since this is a patient-participation survey and not an experimental study, the only alternative to participation is to not participate.

13 Quality Assurance and Supervision by Authorities

This study will be conducted in accordance with elements of E6 Good Clinical Practice Consolidated Guidance, ICH, April 1996, abbreviated requirements of 21 CFR 812.2(b) for Non-significant Risk (NSR) device studies, the Declaration of Helsinki, the Belmont Report, and IRB/EC requirements.

All documents and data shall be produced and maintained in such a way to assure control of documents and data to protect the patient's privacy as far as reasonably practicable. The Sponsor and representatives of the FDA or other regulatory authorities are permitted to inspect the study documents (e.g., study protocol, CRFs, and original study-relevant medical records/files) as needed. All attempts will be made to preserve patient confidentiality.

The clinical site is subject to audit by study sponsor personnel or designee for protocol adherence, accuracy of CRFs and compliance with applicable regulations. Any evident pattern of non-compliance with respect to these standards will be cause for corrective action.

The study protocol, data-recording procedures, data handling as well as study reports are subject to an independent clinical Quality Assurance audit by the study sponsor, its designee, or health authorities.

14 Ethical Considerations

The rights, safety and well-being of clinical investigation subjects shall be protected consistent with the ethical principles outlined in the Declaration of Helsinki. This shall be understood, observed and applied at every step in this clinical investigation.

It is expected that all parties will share in the responsibility for ethical conduct in accordance with their respective roles in the investigation. The Sponsor and the Investigator shall avoid improper influence or inducement of the patient, study monitor, clinical investigator or other parties participating in or contributing to the clinical investigation.

15 Patient Confidentiality

At all times throughout the clinical investigation, confidentiality will be observed by all parties involved. All data shall be secured against unauthorized access. Privacy and confidentiality of information about each patient shall be preserved in the reports and in any publication. Each patient participating in this study will be assigned a unique identifier. All CRFs will be tracked, evaluated, and stored using only this unique identifier.

The study site will maintain a confidential study patient list (paper or electronic) identifying all enrolled patients. This list will contain the assigned study patient's unique identifier and name. The Site Principal Investigator (PI) bears responsibility for keeping this list confidential. This list will not be provided to the study sponsor and is only to be used at the study center.

Monitors and auditors will have access to the study patient list and other personally identifying information of study patients to ensure that data reported in the CRF corresponds to the person who signed the ICF and the information contained in the original source documents. Such personal identifying information may include, but is not limited to the patient's name, address, date of birth, gender, race and medical record number.

NOTE: The patient's name, medical record number or address will NOT be recorded in the monitor's visit report or the database; demographic data that may be recorded includes age, race, and gender.

Any source documents copied for monitoring purposes by the Sponsor will have patient identifiable information redacted and be identified by using the assigned patient's unique identifier in an effort to protect patient confidentiality.

16 Data Analysis and Data Monitoring

The study sponsor or designated clinical research associate or professional, shall monitor the site regulatory study documents and study data as needed. All study records including the completed patient satisfaction questionnaires shall be maintained in a secure location in the investigator's clinic and handled in a manner that maintains confidentiality of the data. Data analysis shall be performed by the study statistician using appropriate analysis tools.

17 Data Storage and Confidentiality

All study records including the completed patient satisfaction questionnaires shall be maintained in a secure location in the investigator's clinic and handled in a manner that maintains confidentiality of the data.

18 Definitions and Acronyms

Adverse Events

Adverse Event (AE) – any untoward medical occurrence in a subject (ISO 14155).

NOTE: This definition does not imply that there is a relationship between the adverse event and the device under investigation.

Serious Adverse Event (SAE) - an adverse event that (ISO 14155):

- led to a death,
- led to a serious deterioration in the health of the subject,
- resulted in a life-threatening illness or injury,
- resulted in a permanent impairment of a body structure or a body function,
- required hospitalization or prolongation of existing hospitalization,
- resulted in medical or surgical intervention to prevent permanent impairment to body structure or function,
- led to fetal distress, fetal death, a congenital abnormality, or birth defect.

Adverse Device Effect (ADE) - any untoward and unintended response to a medical device (ISO 14155)

NOTE: This includes any event resulting from insufficiencies or inadequacies in the instructions for use or the deployment of the device. This definition also includes any event that is a result of user error.

Serious Adverse Device Effect (SADE) – an adverse device effect that has resulted in any of the consequences characteristic of a serious adverse event or that might have led to any of these consequences if suitable action had not been taken or intervention had not been made or if circumstances had been less opportune (ISO 14155).

Anticipated Adverse Device Effect (AADE) – an adverse device effect which by its nature, incidence, severity or outcome has been previously identified in the previously identified in nature, severity, or degree of incidence in the investigational plan or application

Unanticipated Adverse Device Effect (UADE) – any serious adverse effect on health or safety or any life-threatening problem or death caused by, or associated with, a device, if that effect, problem, or death was not previously identified in nature, severity, or degree of incidence in the investigational plan or application (including a supplementary plan or application), or any other unanticipated serious problem associated with a device that relates to the rights, safety, or welfare of subjects (21CFR812.3.s and ISO 14155).

NOTE: The occurrence of a diagnostic or elective surgical procedure for a pre-existing condition, unless the condition becomes more severe or increases in frequency, would not be considered procedure or device-related.

Adverse Device Effect (ADE)

See Adverse Events.

Case Report Form (CRF)

Printed, optical or electronic document designed to record all of the protocol required information to be reported to the sponsor on each trial subject

Confidentiality

Prevention of disclosure, to other than authorized individuals, of a sponsor's proprietary information or a subject's identity (GCP Consolidated Guidance).

Ethics Committee (EC) / Institutional Review Board (IRB)

Synonyms. An independent body constituted of medical, scientific and nonscientific members, whose responsibility is to ensure the protection of the rights, safety and well-being of human subjects involved in a trial by, among other things, reviewing, approving, and providing continuing review of trials, of protocols and amendments, and of the methods and material to be used in obtaining and documenting informed consent of the trial subjects (GCP Consolidated Guidance).

Good Clinical Practice (GCP)

An international quality standard for conducting clinical trials that is provided by International Conference on Harmonisation (ICH) to protect trial subjects rights, safety, and welfare, as well as provide integrity to the overall study data.

Informed Consent

The process by which a subject voluntarily confirms his or her willingness to participate in a particular trial, after having been informed of all aspects of the trial that are relevant to the subject's decision to participate. Informed consent is documented by means of a written, signed and dated consent form (GCP Consolidated Guidance).

Informed Consent Form (ICF)

A document disclosing the risks, benefits, and alternatives of a clinical trial and documents the subject's voluntary willingness to participate in a clinical trial.

Monitoring

The act of overseeing the progress of a trial, and of ensuring that it is conducted, recorded and reported in accordance with the protocol, procedures and the applicable regulatory requirements.

Patient and Observer Scar Assessment Scale (POSAS)

The POSAS is a comprehensive scale that deals with the most commonly described scar characteristics from a patient and observers perspective

Serious Adverse Device Effect (SADE) See Adverse Events. Serious Adverse Event (SAE) See Adverse Events.

Source Data

All information in original and identified records and certified copies of original records of clinical findings, observations, or other activities in a clinical investigation, necessary for the reconstruction and evaluation of the clinical investigation. Source data are contained in source documents (ISO 14155 and GCP Consolidated Guidance).

Source Documents

Original documents, data and records (ISO 14155).

NOTE: This may be, for example, hospital records, laboratory notes, pharmacy dispensing records, copies or transcriptions certified after verification as being accurate copies, photographic negatives, radiographs, and records kept at the pharmacy, at the laboratories, and at medico-technical departments involved in the clinical investigation.

Unanticipated Adverse Device Effect (UADE)

See Adverse Events.

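### The plan names two different raters for the observer part of POSAS, the primary endpoint, and neither defines the impartial rater nor describes masking

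*Combined protocol and SAP*

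**What the plan says.** The synopsis makes POSAS at 6 weeks the primary endpoint. The plan describes who scores it in three places:

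- Section 6.6, text: "the subject and investigator will rate commonly described scar characteristics from a patient and observers perspective".
- Section 6.6, Table 1, for the 3-week and 6-week visits: "POSAS: Subject and Impartial rater Assessment".
- Section 11, steps 6b (3 weeks) and 7b (6 weeks): "POSAS will be performed by an impartial rater".

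Steps 6b and 7b stand in lists of clinic staff tasks; the second list is introduced by "6-week post-operative clinic visit, clinic staff will". Section 6.3 says: "A study staff member will open a sealed randomization envelope consisting of closure assignment". Section 9 says: "Each adverse event will be judged by the Investigator as to its relationship and level of relatedness to the closure device". Table 1 schedules "Adverse Event review" at the same two visits as POSAS. Section 12 adds: "The Investigator has received sponsor-led training in proper use of the device".

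The POSAS entry in Section 18 mentions an observer's perspective but does not say who the observer is. The design statement in Section 5 contains no masking term.

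**The concern.** The documents give two rules for who scores the observer part of the primary endpoint. Under one of them the scorer would ordinarily know the treatment arm. Scar ratings are subjective, so a rater who knows the closure method can shift scores between arms without intending to (detection bias). No masking of subjects is described, so the patient part must be taken as unmasked. The observer part is the one that can realistically be protected.

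Aligning the wording would not settle the matter, because the plan does not say what makes a rater impartial. A staff member who opened the envelope or was present when the device came off could rate without breaching any stated rule.

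**Working it through.** **Comparing the texts**

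1. *Who rates.* The Section 6.6 text says the investigator. Table 1 and Section 11 (steps 6b and 7b) say an impartial rater. No section says that the investigator is the impartial rater, or that one statement overrides the other.
2. *Would the investigator know the arm?* Section 9 has the investigator judge the relatedness of each adverse event to the closure device, which ordinarily requires knowing which device was used. Table 1 puts that review at the POSAS visits. The training in Section 12 shows only familiarity with the product. The documents do not say that the investigator personally applies or removes the closure, and this point does not rely on it.
3. *Does the impartial-rater rule protect the rating as written?* Not reliably. The term is undefined, the steps sit among clinic staff tasks, and a study staff member opens the envelope (Section 6.3). Section 11, step 6, places the 3-week rating directly after device removal, so a rater present at removal would know the arm.
4. *Is masking feasible at the primary time point?* It appears so. Sections 3.1 and 11 have the device removed at 3 weeks, so it should be off at the 6-week rating.

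**Illustration of size**

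Inputs from Section 10: delta 1.5, SD 1.41, alpha 0.05, power 0.9, 19 per group, 5% loss. Two-sided testing is an assumption, since the plan does not state it.

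The plan's own figure comes first. The two-sample normal formula gives n = 2 × (1.960 + 1.282)² × (1.41/1.5)² = 18.6, so 19 per group, or 38 in total; 38/0.95 = 40. This reproduces Section 10. Power of the t test at 19 per group is 0.891. Section 10 calls the data paired, but the paired normal formula gives 9.3, so 10 pairs, and 19 pairs would have power 0.992. The figures therefore fit independent groups with 1.41 as the between-subject SD, and that reading is used here.

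Now suppose there is no true difference but ratings shift by b points between arms. The standard error is 1.41 × √(2/19) = 0.457. The noncentrality parameter is b/0.457, with 36 degrees of freedom. The probability that the two-sided t test rejects is:

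| Assumed shift b (points) | Share of planned delta | Rejection rate |
|---|---|---|
| 0 | 0 | 5.0% |
| 0.25 | 1/6 | 8.3% |
| 0.31 | about 1/5 | about 10% |
| 0.50 | 1/3 | 18.6% |
| 0.75 | 1/2 | 35.8% |

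A simulation of 200,000 runs at b = 0.5 also gave 0.186. If 1.41 were instead the SD of 19 paired differences, the 0.5-point shift would give 0.310.

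**The case against.** The strongest reply is that the plan clearly intends an impartial rater. Table 1 and both visit steps say so, and one descriptive sentence says otherwise. Steps 6b and 7b also break the grammar of their lists and can be read as naming someone outside the clinic staff. This is fair: Section 6.6 may be loose wording, and investigator rating should not be read as the settled plan. It is still a stated rule that a site could follow, and correcting it leaves the term undefined.

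A second reply is that the unmasking routes are inferred. No text links the envelope opener to rating, and the relatedness duty bears only on subjects who have an adverse event. That is also correct. The point is that the plan does not rule these routes out, not that they will occur.

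Third, the illustration may overstate the effect. The shifts are assumed. Section 10 does not say whether its delta and SD refer to the observer, patient, combined or single-item score. If the primary score averaged the patient and observer parts equally, a 0.5-point observer shift would become 0.25, and with the same SD the rate would be about 8% rather than 19%. This stands, so the percentages are not used to support the finding.

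Finally, the benefit is limited. The patient part of POSAS and the satisfaction endpoint are unaffected by who the observer is. Skin marks, or the subject, may still reveal the closure.

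**Conclusion.** The concern holds. The contradiction, the missing definition and the absence of any described masking are all plain in the text, and confidence in them is high. The point does not invalidate the trial, because most of the operational text already calls for an impartial rater. It should nevertheless be corrected, because it concerns who scores part of the primary endpoint.

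The size of any bias is unknown. The illustrative rates of about 8% to 36%, for shifts of 0.25 to 0.75 points, rest on a two-sided test, independent groups, SD 1.41 applied to a single observer score, and no true difference. Section 5.3 plans t tests across POSAS attributes, so these are rates for one score and not for the trial. The SD of a single attribute may differ from 1.41.

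**What to change.** In Section 6.6, replace the investigator with the impartial rater. In Sections 6.6 and 11 (steps 6b and 7b), define that rater as a person who:

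- did not open the randomization envelope;
- did not apply or remove the closure and was not present at either;
- is not told the assignment;
- has no access to the procedure CRF or the procedure-day closure photograph before completing the 6-week rating;
- does not administer or see the satisfaction questionnaire, and does not conduct the adverse event review, before completing that rating.

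At 3 weeks the rater should enter only after removal is finished. Ask subjects not to reveal their closure, and record whether the rater believes the arm was revealed. Steps 6b and 7b should also mention the subject's own POSAS rating, as Table 1 does. If the site has no suitable person, state in the protocol and the report that the observer part is unmasked.

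The cost is a short amendment to two sections, with no change to the sample size. At a single center, the site must check that its planned rater meets the definition or name another person, and must schedule the 3-week rating around device removal. Masking may remain incomplete, because Section 12 lists skin stripping, pigment change and blistering as possible effects and subjects may disclose their closure. The patient part stays unmasked.

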5.2 Sample Size

Knee Arthroplasty of 40 subjects will be enrolled. 20 subjects will receive ZipLine and 20 subjects will receive Staples.

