5.3 Statistical Analysis Plan

General Summary

All variables of interest including subject demographics, baseline characteristics, POSAS scores and patient satisfaction of closure method used will be summarized descriptively by assigned closure groups. Mean, standard deviation, range, and Coefficient of Variation (CV) will be reported across the POSAS Scale attributes, plus comparative "t" test applied between the treatment groups across POSAS attributes. Results will include significance testing (t test) for Knee Arthroplasty study.

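### Does the paired-data label in Section 10 mean that the sample size was worked out for the wrong design?

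*Combined protocol and SAP*

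**What the plan says.** Section 10 (Study Size Determination) introduces the calculation as "Zipline to Staples (2 groups, paired data) with POSAS Scale data", with an estimated difference of about 1.5, an estimated SD of about 1.41 and an alpha of .05. Its result is "Power = 0.9, sample n = 19 pairs, or 38 total subjects". After an allowance of 5% for loss it gives "n = 40 total subjects, or 20 per group". It does not say whether alpha is one- or two-sided, what kind of SD 1.41 is, or which POSAS score the inputs describe.

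The design sections describe separate groups:

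- Section 5.2: "20 subjects will receive ZipLine and 20 subjects will receive Staples".
- Section 6.3: a staff member will "open a sealed randomization envelope consisting of closure assignment and a subject study identification number", and "Subjects will be assigned in consecutive order in a 1:1 ratio for closure assignment".
- Section 11, item 4: "Randomization will be assigned in permuted block so that even numbers of each closure method is assigned".
- Section 5.3: a t "test applied between the treatment groups across POSAS attributes".

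**The concern.** Paired data has a definite statistical meaning: two measurements linked within a subject or a matched set, analysed through their differences. This trial produces no such data. Each subject receives one closure method. Permuted blocks balance the numbers per arm but match nobody, and the plan mentions no bilateral knees, split incisions or matching.

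Two things could be at stake. First, a paired calculation uses the SD of differences, while a comparison of independent groups uses the between-subject SD. If the wrong kind of SD had gone in, 40 subjects might not give the stated power. Second, Section 5.3 is brief and does not use the words independent samples, so an analyst might take Section 10 as licence for a paired test.

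**Working it through.** **Inputs (Section 10).** Difference d = 1.5, SD s = 1.41, alpha = 0.05, power = 0.90, loss 5%. Two-sided alpha is an assumption, tested in step 2.

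**1. Reproduce the plan's figures as two independent groups (normal approximation).**

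n per group = 2 × (1.960 + 1.282)² × s² / d² = 2 × 10.507 × 1.988 / 2.25 = 18.57, so 19.

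Total 2 × 19 = 38. Allowing for loss, 38/0.95 = 40, or 20 per group. All three stated totals match.

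**2. Try the other simple readings.**

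| Reading | Needed for 90% power | Gives 19? |
|---|---|---|
| Two groups, one-sided | 15.13, so 16 per group | No |
| Paired, 1.41 = SD of differences, normal | 9.28, so 10 pairs | No |
| Paired, 1.41 = SD of differences, t | 12 pairs | No |

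If 1.41 were the SD of differences, 19 pairs would give 99.2% power. For 19 pairs to give exactly 90%, that SD would have to be 1.91 (t) or 1.5 × √19 / 3.2415 = 2.02 (normal).

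**3. One paired route does give 19.** Suppose 1.41 is a per-subject SD placed in a paired formula with within-pair correlation r. The SD of differences is then 1.41 × √(2(1 − r)).

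- r = 0: SD of differences 1.99; the normal formula gives 18.57, so 19 pairs.
- r = 0.1: SD of differences 1.89; the t calculation gives 19 pairs.

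The arithmetic therefore cannot prove which formula was used. On this route, however, 1.41 is still a per-subject SD, which is what the between-group test needs, so the sample size is unaffected.

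**4. Power of the planned test, two-sample t, s = 1.41.**

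- 19 + 19 evaluable: 89.1%.
- 20 + 20 evaluable: 90.6%.
- 19 + 19 with d = 1.45: 87.0%; with d = 1.55: 90.9%.

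The shortfall of 0.9 points at 19 + 19 comes from using the normal approximation, not from the paired label. It is smaller than the movement caused by rounding d to one decimal.

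**5. What if 1.41 really were an SD of differences?** Step 2 argues against this. The correlation is an assumption, because the documents give none. The between-subject SD would be 1.41 / √(2(1 − r)).

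| r | Between-subject SD | Two-sample t power at 19 + 19 |
|---|---|---|
| 0 | 1.00 | 99.5% |
| 0.1 | 1.05 | 99.0% |
| 0.3 | 1.19 | 96.5% |
| 0.5 | 1.41 | 89.1% |
| 0.7 | 1.82 | 69.6% |

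Power falls below the 89.1% of step 4 only when r exceeds 0.5. At r = 0.7, 32 per group would be needed for 90%.

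**6. Could the label alter the analysis?** A paired t test needs a variable that links each Zip subject to a Staples subject. The plan defines none. Section 5.3 sets the comparison between treatment groups and summarises results by assigned group. Section 10 itself counts 38 and then 40 subjects at 20 per group, whereas 19 within-subject pairs would be 19 subjects.

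**The case for a change.** The strongest case for acting is that the contradiction is plain and cheap to cure. Paired data remains wrong even if pairs is read loosely as one subject from each arm. Section 5.3 is a single paragraph that says only t test, so naming the independent-samples test would close off any later choice between tests. The label also obscures what 1.41 is, and if it were an SD of differences with a high correlation, the trial would be underpowered.

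The contradiction stands, and tidying the words would do no harm. The rest carries little weight. A between-group t test on unlinked subjects is the independent-samples test, so naming it adds clarity but changes nothing. The underpowered case needs both an SD reading that the stated 19 does not support and an assumed correlation above 0.5; lower correlations give power of 96.5% or more at r = 0.3 and below. The sidedness of alpha and the choice of POSAS score are details left unstated, separate from the paired label. The arithmetic points to two-sided alpha, since a one-sided test would need 16 per group.

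**Conclusion.** The label in Section 10 is a clerical slip, and no change to the plan follows. The totals 19, 38 and 40 are right for the parallel-group design that the other sections describe, and the planned test is already a between-group test. Correcting the label would change neither enrolment, analysis nor conclusion.

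Two assumptions carry this. Alpha is taken as two-sided, which the figures support. The value 1.41 is taken as the within-group SD, which fits the totals exactly but is an inference. If it were an SD of differences, the adequacy of 40 subjects would depend on an unstated correlation, so the statement that n stands is conditional on that reading. That the label contradicts the design is certain; that the calculation began as a two-sample formula is only likely.
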